12.3.1.6.8. Reporting to Regulatory Agency, Institutional Review Board and Site

The sponsor or its designee is responsible for notifying the relevant regulatory authorities of related, unexpected SAEs.

In addition, the sponsor or its designee is responsible for notifying active sites of all related, unexpected SAEs occurring during all interventional studies across the development program.

The investigator is responsible for notifying the local IRB or the relevant local regulatory authority of all SAEs that occur at his/her site, as required.

12.3.2. MDGN-002 Concentration, Pharmacokinetic and Anti-Drug Antibody Assessments

The name and address of the bioanalytical laboratory for this study is defined in the Laboratory Manual(s) and guidance(s).

Pharmacokinetics will be calculated from the plasma concentrations of MDGN-002.

12.3.2.1. Blood Sample Collection and Analysis

Blood samples will be collected within 60 minutes prior to the administration of MDGN-002 on Days 0, 14, 28 and 42 (Visits 2, 4, 6, and 8 respectively) and at any time on Days 7, 21, 35, 49, 56, and 84 (Visits 3, 5, 7, 9, 10, and 11) and processed to plasma (see laboratory manual). Time of PK samples will be recorded in the electronic CRF. A total of 1.0mL plasma (0.5 mL per PK and ADA sample) will be collected from each subject to measure plasma concentrations of

MDGN-002 or ADA samples. Pharmacokinetic and ADA samples will be processed according to the methods and directions set forward in the Laboratory Manual(s) and guidance(s).

Pharmacokinetic and ADA plasma sample analysis will be performed by laboratory defined in the Laboratory Manual(s) and guidance(s), according to their SOPs using a validated enzyme-linked immunosorbent assay (ELISA). Assay and analysis details will be described in the method validation and bioanalytical information.

12.3.3. Assessment of Efficacy

12.3.3.1. Crohn's Disease Activity Index

The CDAI will be completed by a qualified licensed physician, physician's assistant, or a nurse practitioner at the times shown in the Schedule of Assessments (see [Table 1](#)). Site personnel conducting the CDAI should use the following link to derive individual and total scores:

[https://www.thecalculator.co/health/Crohn's-Disease-Activity-Index-\(CDAI\)-Calculator-1035.html](https://www.thecalculator.co/health/Crohn's-Disease-Activity-Index-(CDAI)-Calculator-1035.html), with standard weights calculated as follows:

- Standard weight for men = (height in m)² x 22.1
- Standard weight for women = (height in m)² x 20.8

Information on abdominal pain and frequency of loose and watery stools should be taken from subject diary information (see [Section 12.3.3.4](#)). The same individual should complete the CDAI for a given subject throughout the study, whenever possible.

The CDAI was developed by the National Cooperative Crohn's Disease Study group and published in 1976 by [Best et al \(1976\)](#) to determine variables that best predicted disease activity. A total of 8 items were identified (abdominal pain, number of liquid stools, general well-being, extraintestinal complication, use of antidiarrheal drugs, abdominal mass, hematocrit, and body weight). Each item is scored on individual parameter criteria. Total CDAI scores can range from 0 to approximately 600 with higher scores indicating more active disease. The CDAI has been the most frequently used efficacy scale for interventional trials in CD ([Sostegni et al, 2003](#)).

12.3.3.2. Modified Mayo Score

The Modified Mayo Score (excluding the PGA component) includes stool frequency, rectal bleeding, and the appearance of mucosa upon endoscopy. Stool frequency will be based on a scale of 0 to 3 (0 = normal, 1 = 1 to 2 stools/day > normal, 2 = 3 to 4 stools/day > normal, 3 = > 4 stools/day > normal). Rectal bleeding will be based on a scale of 0 to 3 (0 = none, 1 = streaks of blood, 2 = obvious blood, 3 = blood alone passed). Appearance of mucosa upon endoscopy will be based on a scale of 0 to 3 (0 = normal, 1 = mild friability, 2 = moderate friability, 3 = exudation, spontaneous bleeding). The score consists of the sum of all 3 criteria and can range from 0 to 9, with higher scores indicating more severe disease. This score will be calculated at Visit 1 and Visit 10 using the endoscopy score from the central reader, self-reported data on stool frequency and rectal bleeding from the period prior to the subject being screened for Visit 1 and data from the patient diary for Visit 10.

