^q Subjects requiring wash-out will have a blood test performed at 8 weeks after the start of the wash-out period to confirm the previous biologic therapy is undetectable. If there is no previous biologic therapy detected, subjects will be able to continue onto Visit 2 and will not be required to complete the full 12-week wash-out. If there are detectable levels of the previous biologic therapy, then subjects will complete the full 12-week wash-out before proceeding to Visit 2. For subjects receiving certolizumab pegol (Cimzia) a 12-week wash-out is required.

^r The Modified Mayo Score includes stool frequency, rectal bleeding, and the appearance of mucosa upon endoscopy. This score will be calculated at Visit 1 and Visit 10 using the endoscopy score from the central reader, self reported data on stool frequency and rectal bleeding from the period prior to the subject being screened for Visit 1 and data from the patient diary for Visit 10.

BP=blood pressure; CBC=complete blood count; CDAI=Crohn's Disease Activity Index; CRP=C-reactive protein; DcR3=decoy receptor 3; GGT=gamma-glutamyl transferase; ECG=electrocardiogram; ET=early termination; hCG=human chorionic gonadotropin; LIGHT=Lymphotoxin-like, exhibits Inducible expression, and competes with Herpes Virus Glycoprotein D for Herpesvirus Entry Mediator, a receptor expressed by T lymphocytes; PK=pharmacokinetic; PPD = purified protein derivative; RR=respiration rate; T=temperature; TB=tuberculosis; TNF α =tumor necrosis factor alpha.

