12.1. Study Periods and Visits

12.1.1. Screening (Visit 1)

The subject must be screened within 14 weeks before enrollment in the study. The following procedures will be performed at screening:

1. Obtain written informed consent
2. Review inclusion/exclusion criteria
3. Conduct genotyping for DcR3 genes (CD only)
4. Collect demographic information
5. Record medical and medication history
6. Perform a complete physical examination, including measurements of weight
7. Collect vital signs, including systolic and diastolic blood pressures, pulse, respiration rate and temperature
8. Perform 12-lead ECG
9. Collect blood samples for clinical laboratory tests
10. Perform QuantiFERON-TB Gold (QFT) blood test, or PPD tuberculosis skin test. If the subject's PPD tine skin test is ≥ 5 mm, a confirmatory chest x-ray is required.
11. Collect blood sample for β -hCG test (for females of childbearing potential only)
12. Collect stool sample for *C. difficile* and fecal calprotectin analyses
13. Collect urine sample for urinalysis
14. Collect urine sample for drug testing as warranted
15. Administer the CDAI (CD only)
16. Administer the IBD-Q questionnaire
17. Conduct the endoscopy with biopsy

18. Assess and record any AEs and concomitant medications
19. Provide access to patient diary to record daily assessment of the following:
 - a) Abdominal pain, general well-being and number of stools including loose or watery stool (e.g., 6 or 7 on Bristol stool form scale) and daily abdominal pain severity (scale of 0 to 10) for CD patients.
 - b) Stool frequency and rectal bleeding for UC patients.
20. Calculate the Modified Mayo Score (excluding the PGA component) using the endoscopy score from the central reader and self-reported data on stool frequency and rectal bleeding from the period prior to the subject being screened.

NOTE: Stool samples may be obtained at any time during the visit. Subjects who fail to meet clinical laboratory entry requirements may be re-tested as part of the screening period. Extensions of the screening window to accommodate clinical laboratories re-testing timeframes (excluding endoscopy with biopsy) are permitted as agreed with medical monitor.

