12.1.5.6. Visit 10 (Day 56 [\pm 3 days])

Subjects will return to the clinic on Day 56 (\pm 3 days), at which time the following procedures will be performed:

1. Perform a complete physical examination, including measurement of weight
2. Collect vital signs, including systolic and diastolic blood pressures, pulse, respiration rate and temperature
3. Perform 12-lead ECG
4. Collect blood sample for clinical laboratory tests
5. Collect blood samples for plasma MDGN-002 concentration, PK and ADA analysis
6. Collect blood sample for exploratory analyses as defined in [Table 1](#)
7. Collect stool for fecal calprotectin analysis
8. Collect urine sample for urinalysis
9. Collect urine sample for urine β -hCG test (for females of childbearing potential only)
10. Administer the CDAI (CD only)
11. Review diary completion
12. Administer IBD-Q questionnaire
13. Conduct the endoscopy and biopsy
14. Calculate the Modified Mayo Score (excluding the PGA component) using the endoscopy score from the central reader and the diary data on stool frequency and rectal bleeding (UC only)
15. Assess and record any AEs and concomitant medications
16. Assess subject response and available results against individual stopping rules criteria defined in [Section 8.5.1](#).

In addition, ongoing AEs from the previous visit will be assessed and any change in their status will be recorded.

NOTE: Stool samples may be obtained at any time during the visit.

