13.1.2. Statistical Analyses

Analyses of efficacy will focus on the Efficacy Population. Results of endpoints (e.g., CDAI, SES-CD, abdominal pain and loose/watery stool frequency and IBD-Q (CD only; Modified Mayo Score, stool frequency, rectal bleeding, endoscopic appearance, and IBD-Q (UC only) will be summarized by visit for each cohort, both as raw scores and the change from baseline value. For CD, the CDAI individual and total scores will be derived programmatically using recorded data from patient diary, responses to CDAI questions, laboratory tests, and physical exam results.

For UC, the Modified Mayo Score individual and total scores will be derived programmatically using recorded data from patient diary and endoscopy results. Quantitative endoscopy and biopsy results will also be summarized for both the Baseline and End of study visits.

Analyses of safety data will be focused on the Safety Population (as defined in [Section 13.1.1](#)).

Safety variables include treatment-emergent AEs (TEAEs), clinical laboratory results, vital signs measurements, ECG results, and physical examination findings.

Adverse events will be coded using Medical Dictionary for Regulatory Affairs (MedDRA). TEAEs are defined as any AE having first onset or worsening in severity after the first administration of IP. TEAEs will be classified by system organ class (SOC) and preferred term and summarized by the number of subjects reporting each event for each cohort and overall.

For clinical laboratory tests, descriptive summaries of actual (absolute) values and change from baseline values will be presented by cohort for each study visit.

Vital signs (systolic and diastolic blood pressure, pulse, and respiratory rate) and ECG results will be summarized by visit and cohort using appropriate descriptive statistics.

Data in this open-label study will be monitored continually and may be analyzed at any time.

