4.2 MODIFIED MAYO SCORE (ULCERATIVE COLITIS PATIENTS)

The Modified Mayo Score (excluding the Physician's Global Assessment [PGA] component) includes stool frequency, rectal bleeding, and the appearance of mucosa upon endoscopy. Stool frequency is based on a scale of 0 to 3 (0 = "normal", 1 = "1 to 2 stools/day > normal", 2 = "3 to 4 stools/day > normal", 3 = "> 4 stools/day > normal"). Rectal bleeding will be based on a scale of 0 to 3 (0 = "none", 1 = "streaks of blood", 2 = "obvious blood", 3 = "blood alone passed"). Appearance of mucosa upon endoscopy will be based on a scale of 0 to 3 (0 = "normal", 1 = "mild friability", 2 = "moderate friability", 3 = "exudation, spontaneous bleeding"). The score consists of the sum of all 3 criteria and can range from 0 to 9, with higher scores indicating more severe disease. This score will be derived programmatically for Visit 1 and Visit 10 using the Modified Mayo Endoscopic score from the central reader and self-reported data on stool frequency and rectal bleeding from 7 days prior to Visit 1 (Screening) and Visit 10 (Day 56/ET).

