5.1 BASELINE AND CHANGE FROM BASELINE MEASUREMENTS

The baseline measurement will be defined as the last non-missing assessment on the day of or prior to first study dose administration (includes all data up to the first dose administration).

Change from baseline will be calculated as:

• (value at analysis visit – baseline value)

A positive change signifies an increase in the measurement while a negative change signifies a decrease.

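### The UC Modified Mayo change from baseline sets pre-screening self-report against diary data for two of its three items, although a mandatory pre-dose diary could supply a like-for-like baseline

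*Protocol*

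**What the plan says.** The Modified Mayo Score adds three items scored 0 to 3: stool frequency, rectal bleeding and endoscopic appearance.

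- **Visit 1 source.** Protocol 12.1.1 (item 20) names these inputs to the score: "endoscopy score from the central reader and self-reported data on stool frequency and rectal bleeding from the period prior to the subject being screened". Table 1, footnote r, likewise specifies "self reported data on stool frequency and rectal bleeding from the period prior to the subject being screened for Visit 1". Diary access is first given at that same visit (12.1.1, item 19).
- **Visit 10 source.** Protocol 12.1.5.6 (item 14) uses diary data. Section 12.3.3.2 puts both sources in one sentence: stool frequency together with "rectal bleeding from the period prior to the subject being screened for Visit 1 and data from the patient diary for Visit 10".
- **Statistics section of the protocol.** Section 13.1.2 makes no exception for Visit 1: "the Modified Mayo Score individual and total scores will be derived programmatically using recorded data from patient diary and endoscopy results".
- **SAP derivation.** SAP 4.2 derives the score for Visits 1 and 10 only, from the central endoscopic score and "self-reported data on stool frequency and rectal bleeding from 7 days prior to Visit 1 (Screening) and Visit 10 (Day 56/ET").
- **SAP baseline.** SAP 5.1: "The baseline measurement will be defined as the last non-missing assessment on the day of or prior to first study dose administration". SAP 8.1.2 lists the change in Modified Mayo Score at Visit 10 as a UC secondary endpoint.
- **Timing.** Protocol 12.1.1: "The subject must be screened within 14 weeks before enrollment in the study". The notes in 12.1.1 and 12.2 allow agreed extensions for laboratory re-testing.
- **Pre-dose diary.** Protocol 8.2.1 and 12.1.2 require at least 7 diary days before dosing. SAP 5.8 anchors the screening diary interval on the first dose date.

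**The concern.** A change score is easiest to interpret when both ends are measured in the same way and the first end lies close to the start of treatment. Here neither holds for two of the three items. The Visit 1 values are the patient's account of days before the diary existed. The Visit 10 values are daily entries, with bleeding scored as the worst of each day (SAP 4.5); the documents state no such rule for the Visit 1 account. Between Visit 1 and first dose a subject may also come off a biologic, and symptoms can move for reasons unrelated to study drug.

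At stake is the reading of the only UC disease-activity composite in an uncontrolled signal-finding study. The SAP handles the Crohn's composite differently: the CDAI is derived at Visit 2 from the preceding 7 diary days (SAP 4.1), so its baseline is a pre-dose diary value.

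**Working it through.** The plan gives no figure to reproduce; sample size rests on feasibility. The check is a cross-reading plus simple arithmetic.

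1. **Which value is the baseline?** The score exists at Visits 1 and 10 only (SAP 4.2). The last pre-dose score under SAP 5.1 is therefore the Visit 1 score.

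2. **Can the Visit 1 items come from the diary?** No. Access starts at Visit 1, while SAP 4.2 looks back over the 7 days before it. Protocol 13.1.2 conflicts with 12.3.3.2 and SAP 4.2 on this point.

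3. **Share of the score affected.** Stool frequency 3 + rectal bleeding 3 = 6 of 9 points.

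4. **Time before first dose.** Share of the Visit 1 to Visit 10 interval that is pre-dose = gap / (gap + 56 days).

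| Visit 1 to first dose | Basis | Pre-dose share |
|---|---|---|
| 8 days | earliest Visit 2 (protocol 12.1.2), assuming the diary starts at Visit 1 | 8/64 = 12.5% |
| 14 days | screening of about 2 weeks (12.2) | 14/70 = 20.0% |
| 56 days | 8-week wash-out, assuming the last biologic dose was at Visit 1 | 56/112 = 50.0% |
| 84 days | 12-week wash-out, same assumption | 84/140 = 60.0% |
| 98 days | 14-week limit (12.1.1), before any extension | 98/154 = 63.6% |

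The ±3-day window at Visit 10 moves these by at most 1.4 percentage points. They describe exposure to the problem and are not estimates of bias. With a pre-dose diary baseline the share is about 0% for the two items.

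5. **Effect on one subject's change.** Let S be the symptom sum from Visit 1 self-report, D the sum from the pre-dose diary, and T the sum at Visit 10. Endoscopy is the same in both versions and cancels:

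   planned change − like-for-like change = (T − S) − (T − D) = D − S.

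6. **Bounds on D − S.** UC entry needs endoscopy of at least 2, bleeding of at least 1 and a total of 5 to 9 (protocol 9.3). With endoscopy 2 there are 9 eligible symptom combinations, and with endoscopy 3 there are 11: 20 in all. S runs from 2 to 6.
   - Total applied at Visit 1 only: D can be 0 to 6, so D − S runs from 0 − 6 = -6 to 6 − 2 = +4. The re-based total runs from 2 to 9.
   - Total re-applied at Visit 2 with diary items: D must be at least 2 (endoscopy 3) or 3 (endoscopy 2), so D − S runs from -4 to +4. The re-based total stays at 5 to 9.

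   Both readings are open. The synopsis ties the total to Visit 1, criterion 4 in section 9.3 names no visit, and inclusion criteria are re-evaluated at Visit 2 (8.2.2).

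7. **Effect on the mean of 6.** A one-level difference in one item in one subject moves it by 1/6 = 0.17 points; in all six, by 6/6 = 1.0.

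8. **Conversion.** SAP 4.5 and 5.8 define 7-day averages, but nothing says whether the average enters the Mayo item as it stands or rounded.

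**The case against.** The strongest reply is that the like-for-like result is nearly in the plan already. By step 5, the like-for-like change is the endoscopic change plus the diary changes in stool frequency and rectal bleeding. SAP 8.1.1 and 8.1.2 plan all three. With unrounded items and the same subjects, the three means add up to the proposed composite mean, so the new output is mainly its spread, median and range. All three criteria are also listed by subject (SAP 8.2.3). This stands, and it limits the gain. It does not correct the composite change that will be tabulated.

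Second, SAP 4.2 aligns the two ends more closely than the protocol does: same 7-day look-back, same 0 to 3 scales, and both called self-reported. This also stands, and no evidence in the documents shows that recall and daily recording give different scores. But one label does not make them one method, and the time gap remains.

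Third, the remedy has its own timing flaw. The planned baseline takes all three items from screening, whereas the proposed one joins screening endoscopy to later symptoms. That is true and should be stated in the SAP. Endoscopy is done only at screening and Visit 10, so the mismatch can be removed only from the symptom items.

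Four stronger readings are tempting but unsupported:
- *UC has no other multi-item efficacy endpoint.* IBD-Q total score is one, with its own Visit 2 assessment before dosing (SAP 4.6, 8.1.2).
- *The composite is biased toward improvement.* Selection on the Visit 1 score makes regression to the mean a reasonable worry, but the documents fix neither direction nor size.
- *A 14-week gap is typical.* Wash-out runs from the last biologic dose and can end at 8 weeks, and the number of UC subjects needing it is unknown. Nor is 14 weeks absolute, since extensions are allowed.
- *The SAP states outright that the pre-dose diary is the baseline for the separate symptom endpoints.* That follows from SAP 5.1 read with 5.8; no single sentence says it.

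**Conclusion.** The point holds as a cheap improvement. The planned change in Modified Mayo Score combines any drug effect with a change of recording method and with symptom change between Visit 1 and first dose, in items carrying 6 of 9 points. Per subject the departure lies within -6 to +4 points if the 5 to 9 total applies at Visit 1 only, or -4 to +4 if it is re-applied at Visit 2. These are limits set by the entry rules, not expected values. The actual size and direction cannot be determined from the documents.

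The consequence is confined to interpreting one secondary, descriptive endpoint in about 6 uncontrolled subjects. No hypothesis is tested, and the UC primary efficacy endpoint, the endoscopic score, is unaffected. The conclusion relies on reading SAP 4.2 literally for the Visit 1 window. Protocol 13.1.2 could be read as putting diary data into the baseline, so the passages need reconciling in any case.

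**What to change.** Before database lock, in SAP 4.2 and 8.1.2:

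1. Define the analysis baseline as the screening central-reader endoscopic score plus stool frequency and rectal bleeding from the 7-day diary before first dose.
2. Derive Visit 10 identically, with the 4-of-7-day rule of SAP 5.7 and one stated conversion of the 7-day average to the item score, rounded or unrounded, the same at both ends.
3. Keep the Visit 1 self-report score for eligibility, in the listing and as a supplementary summary, and show each subject's difference between the two symptom baselines.
4. State the downside: the baseline joins screening endoscopy to later symptoms, and a re-based total may fall below 5. Report how many subjects do.
5. Record the change in SAP section 14, which now lists none.

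At the next protocol amendment, reconcile 12.3.3.2 and 13.1.2 with each other and with SAP 4.2.

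The cost is SAP wording and programming. The pre-dose diary is mandatory, its interval is already derived under SAP 5.8, and the missing-day rule already covers UC diaries. After database lock, SAP section 1 would require the supplementary analysis to be labelled post-hoc. The protocol wording needs IRB approval (14.6) and can wait for the next amendment.

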12.3.3.3. Endoscopy with Biopsy and Histology

All subjects who enroll in the study will undergo an endoscopy with biopsy at screening and again at Day 56 (Visit 10) or at early termination. Screening endoscopies may be performed either as a stand-alone endoscopy for purposes of this protocol or as a clinically-required endoscopy, provided consenting procedures for this study were completed prior to endoscopy.

Endoscopy evaluation for patients with CD will use the SES-CD. The SES-CD is a simple, easy-to-use endoscopic scoring system developed specifically for CD. It assesses 4 variables: size of ulcers, percentage of ulcerated surface, percentage of affected surface and the presence of narrowing across 4 categories per variable on a scale of 0 to 3 ([Daperno et al 2004](#)).

Endoscopic evaluation for patients with UC will use the Mayo Endoscopy Score. The Mayo Endoscopy Score is a simple, easy-to-use scoring system in order to evaluate ulcerative colitis stage, based only on endoscopic exploration.

Biopsies taken at screening will be assessed for histological confirmation of disease. Each subject will have screening and Visit 10/ET biopsy samples retained for evaluation of exploratory parameters (which may include but is not limited to DcR3, LIGHT, HVEM and LT β R) which may occur after trial completion. Further information on endoscopic transmission to the central reader and assessment can be found in the endoscopy manual. Information on biopsy collection requirements for exploratory parameters are found in the study sample guidelines.

12.3.3.4. Patient-reported Assessment of Well-being, Abdominal Pain and Stool Frequency (Crohn's Disease Patients)

All CD subjects who enroll in the study will be required to report their daily assessment of well-being, abdominal pain and stool frequency including loose and/or watery stools via a diary (electronic or hard copy). Abdominal pain will be assessed on a scale of 0 to 3 with higher values indicating greater pain severity. The stool frequency including number of loose and/or watery stools per day, equivalent to a score of a 6 or 7 on the Bristol Stool Scale, will be recorded. Loose stools are described as fluffy pieces with ragged edges, a mushy stool. Watery stools are described as watery, no solid pieces ([O'Donnell et al, 1990](#)).

12.3.3.5. Patient-reported Assessment of Stool Frequency and Rectal Bleeding (Ulcerative Colitis Patients)

All UC subjects who enroll in the study will be required to report their daily assessment of stool frequency and rectal bleeding via a diary. Stool frequency is to be recorded as an increase from “normal” where normal is the subject’s bowel movement pattern when healthy, ideally prior to UC diagnosis or for a 24 hour period during a period of disease remission.

